It is anticipated that the case mix in this study will be approximately 70% low risk/ 30% intermediate prognosis cases, leading to a predicted CyberKnife monotherapy 94% 5 year PSA DFS rate, with a potential range of 82% (0% favorable or low risk prognosis cases accrued) to 98% (100% favorable cases accrued). If the protocol case mix deviates from these percentages, then the protocol DFS rate required to successfully test the primary efficacy hypothesis detailed in Section 2.0 may need to be adjusted accordingly.

Table 2. Toxicity review for HDR-Monotherapy for Prostate Cancer

				>= Gd 3 toxicity	•	
HDR Details	Institution	# pts	Median f/u	Total (%)	GI (%)	GU (%)
6-7.25Gy x 6	CA Endocurie ¹⁸	117	3.3	3	0	3
9.5Gy x 4	Beaumont ¹⁹	95	4.2	8	0	8
7.5Gy x 6	Texas Tech ²⁰	145	5	5-8*	1	4 – 7*
6.5Gy x 6	Gamma West (SLC) ²¹	328	1.2	1	0	1
6Gy x 8-9	Osaka (Japan) ²²	111	2.25	7	1	6
	Totals	796	2.4	6	0 -1	5

^{*3%} acute and 4% chronic grade 3 GU toxicity – It is unclear to what degree acute and chronic grade 3 GU toxicity populations overlap in this study.

Due to short median follow-up, the incidence of >= grade 3 late toxicity is likely underestimated. We project that the incidence of late toxicity will increase by approximately 50% when all data reach 5 years maturity, yielding a projected cumulative 5 year HDR monotherapy grade 3 toxicity incidence of 9% (7-8% GU; 1-2% GI). In this study, biochemical disease-free survival (ASTRO and Phoenix definition), freedom from local recurrence, freedom from distant relapse, clinical disease-free survival, disease-specific survival and overall survival will be recorded. The incidence of grade 3 or higher toxicity and the effect of CyberKnife® radiosurgery on bladder, bowel, and sexual function will be followed and monitored using standardized, patient self-administered questionnaires and compared with results published in peer-reviewed literature for other prostate cancer therapeutic modalities. 17

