2. OBJECTIVES

PRIMARY OBJECTIVES: The primary study goal is to document the efficacy of the CyberKnife procedure, where efficacy is defined by biochemical Disease-Free Survival (bDFS), using Phoenix and ASTRO definitions, at 5 years. This will be accomplished through testing the primary efficacy hypotheses detailed in Sections 1.1.5 and 11.2. Additionally, descriptive statistics will be provided comparing the CyberKnife SRS bDFS rate to published HDR monotherapy bDFS rates reported in the literature. A second primary study goal is to accurately measure the rates of acute and late grade 3-5 gastrointestinal and genitourinary toxicity observed during the five years following CyberKnife SRS for prostate cancer.

SECONDARY OBJECTIVES: to measure the following in the study population: Rates of local failure, distant failure, clinical disease-free survival, disease-specific survival, and overall survival; quality of life (QOL) in generic and organ-specific domains; work effort required in treatment planning and delivery of CyberKnife SRS.

Patients will be followed annually to 10 years, to collect additional data for descriptive analysis.

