We chose N large enough to test the null hypothesis against the alternative hypothesis with power equal to 80% at the one-sided 5% significance level.

Let Z_u denote the upper u-th percentile of the standard normal distribution. Hence $Z_{.05} = 1.645$ corresponding to the one-sided 5% level of significance and $Z_{.20} = 0.84$ corresponds to 80% power. Then the sample size is determined by Formula 1:

$$N = \frac{\left[z_{\beta}\sqrt{\pi_{1}(1-\pi_{1})} + z_{\alpha}\sqrt{\pi_{0}(1-\pi_{0})}\right]^{2}}{\left[\pi_{1} - \pi_{0}\right]^{2}}, \text{ where}$$

 π_1 is the expected proportion of CyberKnife treated patients bDFS at 5 years if the alternative hypothesis is true; the bDFS rate is then expected to equal or exceed 0.94. For purposes of sample size estimation, we require 80% power if $\pi_1 \geq 0.945$. π_0 is the expected lower limit of the 95% confidence interval for π and is set equal to 0.90. Then N= 232. Allowing 8% sample size degradation for lost to follow-up, the sample size must be increased to 232/.92 = 253 subjects.

Primary Safety Objective

The primary safety objective is to establish with 95% confidence that the percentage of CyberKnife treated patients experiencing \geq Grade 3 toxicity is not more than 5% higher than the approximately 9% 5-year rate extrapolated from Table 2, Section 1.15.

With N=232 CyberKnife treated subjects, if the observed \geq Grade 3 toxicity rate equals 9%, then with 95% confidence the "true" rate \leq 12.6%. Since the difference between 12.6% and 9% is less than 5%, the sample size of 232 subjects is more than large enough to meet the primary safety objective.

11.3.1 ACCRUAL RATE: the initial three months while institutions are obtaining IRB approval, therefore we do not expect to meet the targeted monthly accrual rate until after the first three months. The estimated accrual rate is 2 patients per study site per month. Expectations of 5 treating study sites assumes an accrual period of approximately 29 months total.

11.4STATISTICAL METHODS

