11.4.1 PRIMARY OBJECTIVES

1. Efficacy

The lower limit of a one-sided 95% confidence interval for the expected proportion of patients experiencing biochemical disease-free survival (bDFS) is estimated by L, where

$$L = \frac{(2np + Z_{0.05}^2) - Z_{0.05}\sqrt{Z_{0.05}^2 + 4pn(1-p)}}{2(n + Z_{0.05}^2)}$$

Here "p" is the observed proportion of patients experiencing bDFS in either arm of the trial. The CyberKnife intervention will be considered to be effective if this study's result verifies that L is not below 90%.

2. Safety

The upper limit of a one-sided 95% confidence interval for the expected proportion of patients experiencing \geq Grade 3 gastrointestinal and genitourinary toxicity is estimated by U, where

$$U = \frac{(2np + Z_{0.05}^2) + Z_{0.05}\sqrt{Z_{0.05}^2 + 4pn(1-p)}}{2(n + Z_{0.05}^2)}$$

Here "p" is the observed proportion of patients experiencing ≥ Grade 3 gastrointestinal or genitourinary toxicity. The CyberKnife intervention will be considered to be safe if this study's result verifies that U is not more than 5% higher than the literature rate of 9%...

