- 12.5. Below are criteria for early termination of the trial (through 25%,50% and 75% enrollment of 232 patients) should an excessive number of patients experience ≥ Grade 3 gastrointestinal and genitourinary toxicity. This depends upon the number so far enrolled and a criterion that identifies too high a rate. The stopping criteria differ after 58, 116 and 174 patients have been enrolled .Consistent with Section 1.1.5, 2.0 we define an observed ≥ Grade 3 gastrointestinal and genitourinary toxicity rate of over 14% as too high. The statistical requirement is that for up to "m" patients enrolled, the number of observed cases with ≥ Grade 3 toxicity must be few enough so that there is a 95% chance that the "true" rate does not exceed 14%.

≥ Grade 3 toxicity Stopping Criteria				
Participants to	Stop study if the number of patients with grade 3-5 toxicity			
be enrolled: 253	equals or exceeds:			
	Enrollment 1-58: 4 Events			
	Enrollment 1-116: 10 Events			
	Enrollment 1-178: 17 Events			

Page 27 of 52

Regulatory Reporting: Any reports regarding safety issues and potential safety issues will also be provided to Accuray's Regulatory Affairs Department. Such reports will be evaluated and reported to the FDA and all applicable regulatory agencies, as deemed required.

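### The primary 5-year safety test uses a crude proportion with no defined denominator and no rule for incomplete follow-up, so the verdict can turn on how lost patients are counted

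*Combined protocol and SAP*

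**What the plan says.** Section 11.4.1 (Safety) defines U as "The upper limit of a one-sided 95% confidence interval for the expected proportion of patients experiencing" grade 3 or higher GI and GU toxicity. In that formula p "is the observed proportion of patients experiencing ≥ Grade 3 gastrointestinal or genitourinary toxicity". The treatment passes if U "is not more than 5% higher than the literature rate of 9" per cent. Section 12.5 shows that the 5% is meant in absolute points, since it treats an observed "toxicity rate of over 14% as too high".

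Both sides of the comparison are 5-year quantities. Section 2 sets out to measure "gastrointestinal and genitourinary toxicity observed during the five years following CyberKnife SRS for prostate cancer". The benchmark in section 1.15 comes from the HDR monotherapy series in Table 2, "yielding a projected cumulative 5 year HDR monotherapy grade 3 toxicity incidence of 9" per cent.

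Section 11.3 obtains 253 from 232, "Allowing 8% sample size degradation for lost to follow-up", and illustrates the safety precision on 232. Section 11.4.1 does not say what n is. It also gives no rule for a patient lost or withdrawn before 5 years. Section 14.6 says only that patients who withdraw may be asked to continue follow-up. Kaplan-Meier estimation appears only under Survival, a secondary item of section 11.4.2.

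**The concern.** A cumulative 5-year rate needs either 5 years of observation on each patient or a method that allows for shorter observation. The formula in section 11.4.1 has neither, and the plan expects about 1 patient in 12 to be lost.

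The protocol accepts this principle for its benchmark. Of the published series it says: "Due to short median follow-up, the incidence of >= grade 3 late toxicity is likely underestimated". It then raises the incidence by about half, from the 6% total in Table 2 to 6% × 1.5 = 9%. The trial's own rate gets no corresponding allowance. If lost patients stay in the denominator, an adjusted benchmark is compared with an unadjusted estimate, and that favours passing.

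At stake are the error rate of a co-primary safety conclusion and the possibility that n is chosen after the event count is known.

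**Working it through.** **Inputs.** One-sided Z = 1.645, limit 14% and the U formula (11.4.1, 12.5); n = 232 or 253 and 8% loss (11.3). The timing of toxicity relative to loss is not in the documents, so it is varied below.

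**1. The plan's own figure.** U = [2np + Z² + Z√(Z² + 4np(1−p))] / [2(n + Z²)]. With n = 232 and p = 0.09: (41.76 + 2.706 + 1.645 × √78.71) / 469.4 = 12.6%, as section 11.3 states. Also 232/0.92 = 252.2, which rounds up to 253.

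**2. Events allowed.**

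| Events | U, n = 253 | U, n = 232 |
|---|---|---|
| 23 | 12.51% | 13.62% |
| 24 | 12.96% | 14.10% |
| 25 | 13.40% | 14.59% |
| 26 | 13.85% | 15.07% |
| 27 | 14.29% | 15.55% |

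The most events that still pass are 26 on 253 and 23 on 232. Counts of 24, 25 and 26 give opposite verdicts.

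**3. Chance of passing at a true 14% with no loss.** P(X ≤ 26 | 253, 0.14) = 4.9%; P(X ≤ 23 | 232, 0.14) = 4.0%.

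**4. Chance of passing with 8% loss, under three ways of counting.**

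*(a) All 253 in the denominator, lost patients without an event counted as event-free.* Let s be the share of the lost patients' 5-year toxicity that is seen before loss. The expected proportion is 0.14 × (0.92 + 0.08s).

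| Assumption | s | Expected p | P(X ≤ 26) |
|---|---|---|---|
| No toxicity seen before loss | 0 | 12.88% | 12.5% |
| Half seen | 0.50 | 13.44% | 8.0% |
| Constant hazard, loss times uniform over 5 years | 0.51 | 13.45% | 7.9% |
| 3/7 of events acute and all seen, half of the rest seen | 0.71 | 13.68% | 6.5% |

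For the third row, λ = −ln(0.86)/5 = 0.0302 per year. The mean risk accrued before loss is 1 − 0.14/(5λ) = 7.18%, so p = 0.92 × 14% + 0.08 × 7.18% = 13.45%. The 3/7 in the last row is an assumption. It rests on one series in Table 2, whose footnote gives 3% acute and 4% chronic grade 3 GU toxicity with unclear overlap.

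*(b) Completers only, n = 232.* If loss is non-informative, the expected p stays at 14% and the chance of passing stays at 4.0%. Events already seen in lost patients are thrown away.

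*(c) Events before loss kept, event-free lost patients dropped.* With s = 0.5, p = 0.14 × 0.96 / (0.92 + 0.04 × 0.14) = 0.1344/0.9256 = 14.5%. The bias is away from passing.

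**5. Deaths.** A patient who dies without grade 3 toxicity cannot have it later. If every patient is followed to 5 years or death, cumulative incidence with death as a competing event equals the crude proportion of all treated patients. Deaths therefore add nothing to the bias in (a).

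**The case against.** A reader might infer that the plan counts lost or dead patients as toxicity-free and so biases the test toward passing. The documents do not support that. Section 11.4.1 is silent on n, and the only n used for safety is 232, the number left after 8% loss, which points if anything to exclusion. The direction of bias depends on the unstated choice: toward passing in (a), none in (b), away from passing in (c). For deaths, the inference is mistaken in any case (step 5).

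Two further cautions stand. Applying 8% loss to 232 would count the loss twice, so the error figures under (a) belong to 253 only. Attrition above 8% would enlarge the effect, but the documents give no higher rate.

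It can also be said that the effect is small. At a true 9%, the constant-hazard model gives 0.92 × 9% + 0.08 × 4.57% = 8.65%, a shift of 0.35 points against a 5-point margin. Acute events, which section 2 includes, mostly come before loss and reduce the effect further. That is correct away from the boundary. At 14%, where the error rate of the test is defined, the same mechanism takes it from 4.9% to between 6.5% and 8%.

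The 232 in section 11.3 remains an illustration of precision at the efficacy sample size and not an analysis rule. The objection limits the claim about direction but does not supply the missing definition.

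**Conclusion.** The point holds as a defect of method and specification. A co-primary 5-year cumulative endpoint is tested with a crude proportion that has no defined denominator and no treatment of incomplete follow-up.

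The firmest consequence needs no assumption about when events or losses occur: with 24 to 26 events the verdict reverses between 253 and 232. The inflation of the error rate is conditional. It arises only if all 253 are counted with lost patients as event-free, and it assumes 8% loss and a true rate of exactly 14%. On those terms the chance of passing is about 6.5–8% under plausible timing and 12.5% at the extreme, against 4.9% with no loss. The stronger statement, that the plan as written is biased toward safe, is not established. The matter should be corrected, because a standard method removes the ambiguity and makes fuller use of the data than any of the three crude counts.

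**What to change.** In section 11.4.1 (Safety), define the analysis set as all treated patients. Estimate the 5-year cumulative incidence of a patient's first grade 3 or higher GI or GU toxicity. Treat death without such toxicity as a competing event and censor loss or withdrawal at the last toxicity assessment. A grade 5 GI or GU toxicity is itself an event. Compare the one-sided 95% upper limit with 14%, and name the interval method in advance. The crude proportion can be kept as a supporting figure, with its denominator stated.

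The cost is SAP wording, an estimate slightly higher than the all-patients proportion and a slightly wider limit. The method needs toxicity onset dates or, failing those, visit dates. The assessments scheduled in section 9 through year 5 should supply them, but the case report forms are not reproduced in the protocol, so this should be confirmed.

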11.4.2. SECONDARY OBJECTIVES

1. Local and Distant Tumor Control

As defined in Section 9.4, the failure to achieve local and distant tumor control will be documented for each patient. These rates will be summarized and descriptive statistics (standard deviations, confidence intervals) will calculated.

2. Quality of Life Assessments

The SF-12 total score, AUA score, EPIC-26 total score and the EPIC-sexual domain sub score are used to quantify quality of life (QoL) at baseline and repeatedly during the post treatment period (see Section 9.0). We will use the generalized estimating equation (GEE) method to provide valid inferences. This method was originated to make inference about average behavior, where the dependent variable depends not only on the "explanatory" variable (time measured in months) but also on the correlation of a patient's repeated measurements. The GEE approach fits the model to the observed data as closely as possible, weighting each patients' "cluster" of measurements over time inversely to its variance - covariance matrix. With this method, no imputations are required and all data recorded is use in the analysis. Other important features of GEE are that no distributional assumptions for the dependent variable are required to use the method and in most cases valid inferences are provided even when the correlation structure is miss-specified. For each score, we will use GEE to fit a straight line to patients' longitudinal course of repeated values. We hypothesize that immediately following treatment, the GU & GI subsections of the EPIC-26 and the AUA will demonstrate a worsening of GU and GI function, but this will return to normal with time. We further hypothesize that the sexual function subset of the EPIC-26 will show gradual worsening function relative to baseline over the five-year follow-up period. These QOL outcomes will be compared to those reported in other prospective studies using the same instruments, including RTOG 0232

and 0415. We hypothesize that the slope of a fitted line will not be significantly less than zero; that is, QoL will be maintained throughout the assessment period.

3. Adverse Events

All adverse events will be recorded on the case report forms. For both acute (<=90 days of treatment start) and late (>90 days of treatment start), the frequency and proportion of each type of adverse event will be presented in tabular form, on both a per-patient and a per-event basis.

4. Survival

"Survival" is variously defined in Sections 1.1.5, 2.0. Periodically over the extended follow-up period, Kaplan-Meier "survival" curves will be calculated (examples: at 6 months, yearly, 5 years, at end of patient follow-up). From the Kaplan-Meier curve, descriptive statistics will be calculated including estimates of survival rates and mean and quartile survival times.

5.Work Effort

At each site and for each patient, time spent actively involved with planning and treatment shall be recorded for all member of the treatment team (therapist, physicist, radiation oncologist, and urologist). The required on-site supervisory time will also be recorded. Average times will be recorded. Time spent by team members will be compared with other outcomes (e.g. experience level of team member, patient enrollment, treatment planning/delivery QA outcomes, toxicity, bDFS and QOL outcomes) and correlations determined.

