Date of Birth (optional): MonthDay	Year		

	Do Not Mark in This Space
	23/
,	
ne number)	26/
0	4000
e number)	27/
weeks?	
e Big n Problem 4 4	28/ 29/ 30/
4	31/
4	33/
weeks?	34/
	34/

							Mark : This Space
1. Ove	r the past 4 weeks, how often ha	ave you le	eaked urine?				
11 000000	More than once a day						
	About once a day						
	More than once a week			e one numb	er)		23/
	About once a week		4				17.69
	Rarely or never		5				
2. Whic	h of the following best describes	your urin	ary control du	iring the las	t 4 weeks?		
	No urinary control whatsoev	er		1			
	Frequent dribbling			2	(Circle one n	umber)	26/
	Occasional dribbling		***********	3			
	Total control			4			
	many pads or adult diapers per oing the last 4 weeks?	day did yo	ou usually use	e to control le	eakage		
	None			0			
	1 pad per day			1			
	2 pads per day			2	(Circle one n	umber)	27/
	3 or more pads per day			3			
4. How	big a problem, if any, has each o	f the follo	wing been fo	r you during	the last 4 wee	eks?	
	Circle one number on each line)						
a.	Dripping or leaking urine	No Problem 0	Very Small Problem 1	Small Problem 2	Moderate Problem 3	Big Problem 4	28/
b.	Pain or burning on urination	0	1	2	3	4	29/
c.	Bleeding with urination	0	1	2	3	4	30/
d.	Weak urine stream						
	or incomplete emptying	0	1	2	3	4	31/
e.	Need to urinate frequently durin	ıg					
	the day	0	1	2	3	4	33/
5. Over	all, how big a problem has your u			r you during	the last 4 we	eks?	
	No problem						
	Very small problem						
	Small problem			(Circle one	number)		34/
	Moderate problem						
	Big problem,		5				
DEC-SE 6 200	2 Commisht	2002 The	University of M	ichigan All vie	hts reserved		

пппппппп52

a. Urgency to have	No Problem	Very Small Problem	Small Problem	Moderate Problem		
a bowel movement	. 0	1	2	3	4	49
			2	3	4	49
Increased frequency of bowel movements	. 0	1	2	3	4	50
		17.1		>251	600	1.75
Losing control of your stools		1	2	3	4	52
Bloody stools e. Abdominal/ Pelvic/Rectal pain		1	2	3	4	53 54
7. Overall, how big a problem have your			_			
No problem			ou during	tile last 4 we	eksr	
Very small problem						
Small problem			(Cirolo on	number)		55
Moderate problem			(Circle one	number)		55
Big problem						
How would you rate each of the follow						
			Poor to None	Poor Fair	Good Very	
a. Your ability to have an erection	on?		1	2 3	4 5	57
b. Your ability to reach orgasm ((climax)?		1	2 3	4 5	58

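### Section 11.4.2 predicts a course for the EPIC-26 urinary and bowel subsections but specifies no analysis of either domain score, so the bowel prediction has no patient-reported score of its own

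*Combined protocol and SAP*

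**What the plan says.** Section 11.4.2 (Quality of Life Assessments) names four scores: "The SF-12 total score, AUA score, EPIC-26 total score and the EPIC-sexual domain sub score are used to quantify quality of life (QoL". The model is the same for all of them: "For each score, we will use GEE to fit a straight line to patients' longitudinal course of repeated values".

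The paragraph then makes domain-level predictions. Immediately after treatment, "the GU & GI subsections of the EPIC-26 and the AUA will demonstrate a worsening of GU and GI function", followed by a return to normal. For sexual function, "the sexual function subset of the EPIC-26 will show gradual worsening function relative to baseline over the five-year follow-up period". The only hypothesis tied to a model parameter is the last one: "We hypothesize that the slope of a fitted line will not be significantly less than zero".

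A comparison with the literature is also promised: "These QOL outcomes will be compared to those reported in other prospective studies using the same instruments". No method or score is given for it.

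The secondary objective in Section 2 is "quality of life (QOL) in generic and organ-specific domains". The end of Section 1.15 says that bladder, bowel and sexual function will be followed by self-administered questionnaire and compared with published results.

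**The concern.** The analysed scores and the stated hypotheses do not match. The EPIC sexual score appears both in a prediction and in the list of scores, so the plan separates a domain where it means to. The EPIC urinary and bowel scores appear in a prediction only.

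What is at stake is the patient-reported picture of bowel and urinary function after treatment. Section 1.12 itself argues that patient reports detect treatment effects better than physician reports. Section 14.3 lists permanent bowel bother and urinary leakage as less likely effects, a category that Section 14.1.2 defines as up to 20% of patients. Such effects may fall short of grade 3 and so miss the primary safety endpoint. The EPIC bowel and urinary items are the questionnaire items that would show them.

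**Working it through.** The plan gives no figure to reproduce here. The check sets hypotheses against listed scores, then asks whether the EPIC total or the straight line could fill the gap.

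**1. Hypotheses against listed scores (Section 11.4.2)**

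| Prediction | Score named in the prediction | In the list of analysed scores? |
|---|---|---|
| Urinary: worsens, then recovers | EPIC urinary subsection | No |
| Urinary: worsens, then recovers | AUA | Yes |
| Bowel: worsens, then recovers | EPIC bowel subsection | No |
| Sexual: gradual worsening | EPIC sexual subset | Yes |

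The AUA covers only part of urinary function. Its seven items in Appendix VI concern emptying, frequency, intermittency, urgency, stream, straining and nocturia. Leakage, pads, pain and bleeding are asked about in EPIC items 1 to 3 and 4a to 4c.

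**2. Can the EPIC-26 total stand in?**

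Item counts from Appendix VI: urinary 1, 2, 3, 4a–e, 5 = 9; bowel 6a–e, 7 = 6; sexual 8a–b, 9, 10, 11, 12 = 6; hormonal, the five-part last item = 5. The sum is 9 + 6 + 6 + 5 = 26.

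The documents do not say how the total is formed. Assume that every item or domain is on a common 0–100 scale. The change in the total for a 10-point loss confined to bowel is then 10 × the bowel weight:

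- mean of 26 items: 10 × 6/26 = 2.3 points
- mean of four domains: 10 × 1/4 = 2.5 points
- mean of five domains (urinary split in two, an assumption): 10 × 1/5 = 2.0 points

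So 75% to 80% of a bowel-only change does not show in the total.

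**3. Would a straight line answer the prediction once the scores were added?**

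EPIC visits over five years (Sections 9 and 9.1.4) are at t = 0, 1, 6, 12, 24, 36, 48 and 60 months. Assume complete data and an ordinary least-squares line through the mean profile.

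- Σt = 187, Σt² = 7957, Sxx = 7957 − 187²/8 = 3585.875.
- Slope = (Σty − Σt·Σy/8)/Sxx, where y is change from baseline.

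Profile A, full recovery: y = 0, −10, −3, 0, 0, 0, 0, 0.

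- Σy = −13, Σty = −28
- slope = (−28 + 187 × 13/8)/3585.875 = 275.875/3585.875 = **+0.077 per month**

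Profile B, lasting 5-point loss: y = 0, −10, −7, −5, −5, −5, −5, −5.

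- Σy = −42, Σty = −952
- slope = (−952 + 187 × 42/8)/3585.875 = 29.75/3585.875 = **+0.008 per month**

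Both meet the criterion of a slope not below zero, because the early dip pulls the left end of the line down. Nor does the size of the slope help. Scaling profile A by 29.75/275.875 = 0.108, which is a dip of 1.08 points at 1 month and 0.32 at 6 months with full recovery, gives exactly the slope of profile B.

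**The case against.** The strongest reply is that the gap is one of wording, in a secondary objective of a single-treatment study. No success, safety or stopping rule depends on it (Sections 11.4.1 and 12.5). The domain hypothesis is stated prospectively, the items are collected, and the sentence on comparison with other studies can be read as covering the subsections just named. All of this is fair, and it limits the consequence. It does not supply an analysis: none of these places names an EPIC bowel or urinary score with a model, summary or test.

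Several stronger readings are tempting, and the documents do not support them.

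- A reader might infer that bowel function goes unanalysed. Bowel items enter the EPIC total, grade 3 or higher GI events are in the primary safety analysis, and adverse events are tabulated by type.
- A reader might infer that the urinary hypothesis has no score of its own. It names the AUA, which is listed and is collected more often than EPIC.
- A reader might infer that the urinary and bowel hypothesis can never be answered. The domain scores can be derived from data already scheduled.
- A reader might infer from the printed response codes, which run in different directions, that the total is uninterpretable. The plan does not say that the total is a raw sum of those codes, and Section 9.3.2 describes a validated instrument.
- A reader might infer that a bowel loss would be cancelled by gains elsewhere. The plan predicts no domain rising above baseline. Dilution, not cancellation, is the issue.

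**Conclusion.** The point holds as a mismatch between hypothesis and analysis. No separate EPIC-26 urinary or bowel domain analysis is specified. The bowel prediction therefore has no domain-level patient-reported analysis, and the urinary prediction rests on the AUA alone. This falls short of the organ-specific objective in Section 2.

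The mismatch and the item count (6 of 26, or 23%) come straight from the text. The 2.0 to 2.5 points per 10-point bowel loss depend on an assumed equal-weight scoring rule. The slopes depend on assumed mean profiles, complete data and a least-squares fit. They show that a single slope cannot separate recovery from lasting loss; they do not predict what this trial will find.

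**What to change.** In Section 11.4.2:

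1. Add the EPIC-26 urinary and bowel domain scores to the list, alongside the sexual score. State how each score is calculated and which direction is better. On the printed AUA form higher codes mean worse symptoms, so a slope not below zero would not mean that function is maintained on that score.
2. Base the urinary and bowel hypothesis on those two domain scores and the AUA, not on the EPIC total.
3. Report change from baseline with confidence intervals at each scheduled visit, or fit a piecewise time model with separate early and late segments, rather than only one straight line.
4. Name the domain scores that will be used in the comparison with other studies.

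The cost is SAP wording and a few more model runs. EPIC-26 is already scheduled at baseline, at 1, 6 and 12 months, and yearly after that, so no visit, sample size or primary endpoint changes. The downside is a few more secondary outcomes, which should be labelled descriptive.
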